8.3. Data Handling Conventions

By-subject listings will be created for important variables from each eCRF module. Summary tables for continuous variables will contain the following statistics: N (number in population), n (number with data), mean, standard deviation, 95% confidence intervals (CIs) on the mean, median, minimum, and maximum. Summary tables for categorical variables will include: N, n, percentage, and 95% CIs on the percentage. Unless otherwise indicated, 95% CIs for binary variables will be calculated using the binomial distribution (exact method) and will be 2 sided. Data will be described and summarized by dose level, analysis set, and time point if applicable. As appropriate, changes from baseline to each subsequent time point will be described and summarized. Similarly, as appropriate, the best change from baseline during the study will also be described and summarized. Graphical techniques (eg, waterfall plots, Kaplan-Meier curves, line plots) may be used when such methods are appropriate and informative.

The baseline value used in each analysis will be the last (most recent) pre-treatment value. Data from all sites will be pooled for all analyses. Analyses will be based upon the observed data unless methods for handling missing data are specified. If there is a significant degree of non-normality, analyses may be performed on log-transformed data or nonparametric tests may be applied, as appropriate.

Unless otherwise specified, all analyses will be 2-sided at the 0.05 level of significance.

8.4. Demographic Data and Baseline Characteristics

A listing of all full-analysis subjects will be generated to describe site, subject number, first screening date, first treatment date, dose level, duration of study drug treatment, and the reason for discontinuing study treatment. Available information on subjects who were screened but not treated may be listed separately.

Subject demographic and baseline characteristics will be listed and summarized by dose level for the full analysis set.

8.5. Efficacy Analysis

The efficacy will be evaluated per the response criteria in NCCN guidelines on ALL (Appendix 4).

8.5.1. Primary Analysis

Categorical Endpoints

Overall remission rate and other response rate variables will be described. In the analyses of overall remission rate at induction completion, subjects who do not have sufficient baseline or on study tumor assessment to characterize response will be counted as failures. For all analyses, the corresponding 95% exact CIs will be presented.

Time-to-Event Endpoints

RFS, EFS and OS will be analyzed using Kaplan-Meier (KM) methods. The KM estimate of the survival function will be computed and the results will be presented using KM curves. The median will be provided along with the corresponding 95% CI. Additionally, the 25% and 75% percentiles for these endpoints will also be provided. In addition, the estimated rate at 6 month, 12 month, 2 year and 3 year will be reported.

The following censoring rules will be applied:

RFS: For a subject who is not known to have relapsed or died by the end of the study follow-up or data cutoff, RFS is censored on the date of the last available disease assessment of the subject.

EFS: For subjects with none of the events defined in EFS before the end of the study follow-up or data cutoff, EFS is censored at the date of the last available disease assessment of the subject.

OS: For a subject who is not known to have died by the end of study follow-up or data cutoff, OS is censored on the date the subject is last known to be alive.

Analysis of remission duration will be analyzed using cumulative incidence by considering death without relapse as competing risks. The estimate of the cumulative incidence of relapse (CIR) will be reported with the associated 95% CI. For a subject with no report of relapse by the end of the study follow-up or data cutoff date, observation is censored on the date of the last available assessment of the subject.

Continuous Endpoints

Continuous endpoints (e.g. TTR and TTC) will be summarized using descriptive statistics.

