1. INTRODUCTION

This statistical analysis plan (SAP) describes the statistical analysis methods and data presentations to be used in tables, figures, and listings (TFLs) in the clinical study report (CSR) for Study GS-US-339-1560. This SAP is based on the study protocol GS-US-339-1560 Amendment 5 dated 13 April 2018 and the electronic case report form (eCRF). The SAP will be finalized before database finalization. Any changes made after the finalization of the SAP will be documented in the CSR.

The study was originally designed to evaluate the safety, efficacy, tolerability, and pharmacokinetics (PK) of entospletinib (ENTO) in combination with vincristine (VCR) and dexamethasone in 2 stages: (1) Phase 1b dose-escalation; (2) Phase 2 expansion for relapsed or refractory Acute Lymphoblastic Leukemia (ALL). However, due to the low response rate to ENTO in combination with VCR and dexamethasone in Phase 1b portion, the Sponsor has decided to not proceed with the Phase 2 portion of this study. Subjects currently on study will continue to be treated and/or followed until the end of study criteria are met. A synoptic CSR will be generated, and this SAP describes the analyses for Phase 1b only.

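### The censoring sentence for cumulative incidence of relapse does not exclude subjects who died in remission, and so contradicts the competing-risk method stated in the same paragraph

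*Protocol*

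**What the plan says.** The relevant text is the time-to-event part of protocol section 8.5.1. The paragraph on remission duration has three sentences.

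- The method: "Analysis of remission duration will be analyzed using cumulative incidence by considering death without relapse as competing risks".
- The output: "The estimate of the cumulative incidence of relapse (CIR) will be reported with the associated 95% CI".
- The censoring rule: "For a subject with no report of relapse by the end of the study follow-up or data cutoff date, observation is censored". The date follows in the same sentence: "observation is censored on the date of the last available assessment of the subject".

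A few lines above, the rule for relapse-free survival applies to a subject "who is not known to have relapsed or died by the end of the study follow-up or data cutoff, RFS is censored". The EFS rule refers in the same way to subjects with none of that endpoint's events.

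The visible SAP efficacy text (sections 6.2.1 and 6.2.2) covers response rates only and has no rule for remission duration. The exploratory text is blank in protocol section 8.1.4 and redacted in SAP section 1.1.3. SAP section 1 limits the scope: "A synoptic CSR will be generated, and this SAP describes the analyses for Phase 1b only".

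**The concern.** A subject who dies in remission has no report of relapse. The method sentence makes that subject a competing event; the censoring sentence makes the same subject a censored observation. Nothing in the paragraph says which prevails. The RFS rule names death and the CIR rule does not, so this looks like a phrase left out by accident.

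The distinction matters because the censoring sentence is the one most likely to be turned into code. It is the only sentence in the paragraph that assigns a status and a date, and it gives no date for a death. Once deaths in remission are censored, the analysis has no competing events left. The relapse curve then describes a setting in which those subjects could still have relapsed, and it is reported under the name of a quantity that it does not estimate.

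The case can occur. Long-term follow-up (protocol section 6.7.2) collects survival, other malignancies and ALL treatments, and schedules no disease assessment. A known death with no relapse on record, some time after the last assessment, is therefore a possible data pattern. The documents do not say how often to expect it.

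**Working it through.** **Side by side.** Every subject in remission ends in one of three states.

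| State at end of follow-up or cutoff | Method sentence | Censoring sentence |
|---|---|---|
| Relapse reported | event | event |
| Died, no relapse reported | competing event | censored at last assessment |
| Alive, no relapse reported | (silent) | censored at last assessment |

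The sentences collide only in the second row.

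**Plan figures.** The documents give no CIR value, number of remitters, relapse rate or rate of death in remission. There is no figure to reproduce, and every number below rests on assumed data.

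**Six-responder illustration.** Assumed: deaths without relapse at months 2 and 4, relapses at months 3 and 6, two subjects relapse-free at month 12.

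*Deaths as competing events (Aalen-Johansen).* Each relapse adds S/n, where S is the proportion still alive and relapse-free just before it and n is the number at risk.

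- Death at month 2: S = 5/6.
- Relapse at month 3, n = 5: adds (5/6)(1/5) = 1/6; S = (5/6)(4/5) = 4/6.
- Death at month 4, n = 4: S = (4/6)(3/4) = 3/6.
- Relapse at month 6, n = 3: adds (3/6)(1/3) = 1/6.
- CIR = 1/6 + 1/6 = 33.3%.

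*Deaths censored on the date of death.* The numbers at risk at the two relapses are 5 and 3, so 1 − (4/5)(2/3) = 1 − 8/15 = 46.7%.

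*Deaths censored at the last assessment, as the sentence says.* If the subject who died at month 4 was last assessed before month 3, the numbers at risk are 4 and 3, so 1 − (3/4)(2/3) = 50.0%. If that subject was assessed between months 3 and 4, the result stays at 46.7%.

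The difference is therefore 13.4 to 16.7 points in this example (46.7 − 33.3 and 50.0 − 33.3, from rounded values). With no deaths in remission the two estimates are the same.

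**Range over assumed rates.** Take constant monthly hazards r for relapse and d for death without relapse. The competing-risk CIR at time t is r/(r+d) × (1 − exp(−(r+d)t)). With deaths censored on the date of death the estimate is 1 − exp(−rt). At t = 12 months with r = 0.06:

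| d per month | Competing-risk CIR | Deaths censored | Difference (points) |
|---|---|---|---|
| 0 | 51.3% | 51.3% | 0 |
| 0.01 | 48.7% | 51.3% | 2.6 |
| 0.03 | 44.0% | 51.3% | 7.3 |
| 0.06 | 38.2% | 51.3% | 13.2 |
| 0.12 | 29.5% | 51.3% | 21.8 |

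Differences are taken before rounding. Over r from 0.03 to 0.12 and d from 0 to 0.12, the 12-month difference runs from 0 to 29.1 points. These hazards are assumptions chosen to show direction and scale; none comes from the documents.

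**The case against.** The strongest reply is that the paragraph already states the right method. Its first sentence calls for "cumulative incidence by considering death without relapse as competing risks". On the natural combined reading, a subject with no relapse who has died is a competing event, and the last sentence deals only with those who have had neither event. An experienced programmer would probably do this without being told. The protocol nowhere says that deaths are to be censored.

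This reply stands in part. A reader might infer that the plan censors deaths in remission and so overstates relapse. The documents do not support that: the stated method is the opposite, and the upward bias arises only if the last sentence is coded literally. What the reply does not remove is the conflict. The censoring sentence has no exception for death, and the RFS rule shows that the authors wrote one where they meant it.

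A second reply is that the analysis hardly matters. CIR is not among the endpoints in protocol sections 8.1.2 and 8.1.3. Dose escalation rests on DLTs and other adverse event data, with no role for CIR. SAP section 1.3 plans 20 subjects in dose escalation, only remitters enter a CIR, and protocol section 3.3.2 reports a low response rate as the reason for not proceeding to expansion. All of this stands, and it sets the severity.

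A reader might also infer from the visible SAP text that the analysis was dropped. That cannot be concluded, because the exploratory text is redacted and the SAP abbreviation list still carries RFS, EFS and OS. For the same reason, the visible text cannot show whether the wording was put right in the removed parts.

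**Conclusion.** The censoring sentence is wrong as written; severity is low. It contradicts the competing-risk sentence in its own paragraph by leaving out the exception for death that the RFS rule contains.

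The consequence is conditional. Coded literally, the estimate is 1 minus Kaplan-Meier. This is never below the competing-risk CIR, and it is above it when a death in remission precedes a later relapse. Using the last assessment as the censoring date can widen the gap, because the subject leaves the risk set earlier. If the competing-risk sentence governs, or if nobody dies in remission, there is no bias.

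The size cannot be found from the documents. The figures of 33% against 47% to 50%, and the 12-month range of 0 to 29.1 points, rest entirely on the assumed data and hazards shown. They should not be read as a forecast for this trial. A reader might take the transplant expectation in protocol section 3.3.3 as evidence that deaths in remission will be common, but that section gives no mortality in remission and does not support the step.

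**What to change.** Replace the censoring sentence in protocol section 8.5.1 with wording to this effect:

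*A subject with neither a reported relapse nor a known death when follow-up ends or at the data cutoff is censored on the date of the last available assessment. Death without relapse is a competing event on the date of death. CIR is estimated with the Aalen-Johansen cumulative incidence function.*

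If the analysis is still planned, put the same rule in the SAP. The protocol already collects relapse, survival and assessment dates, so no data or visit changes. The cost is one reworded rule and a check that the program uses three status codes (relapse, death without relapse, censored). If the analysis has already been programmed, confirm that deaths in remission carry the competing-event code and record the clarification in the CSR.

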8.6. Safety Analysis

All safety data collected on or after the date that study treatment was first dosed up to 30 days after the date of last dose of study treatment will be summarized by dose level.

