6.7.2. Long Term Follow-Up

Long term follow-up for survival will be conducted every 3 months (\pm 4 weeks) after the discontinuation of treatment visit until end of study. Information to be gathered includes ALL treatments, other malignancies, and survival which could be collected during a routine clinic visit, other contact with the subject, or via telephone. Gilead reserves the right to discontinue or shorten the duration of participation in the long term follow-up period at any time.

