7.2.2. Assessment of Severity

The severity of adverse events will be graded using the CTCAE, Version 4.03. For each episode, the highest severity grade attained should be reported.

If a CTCAE criterion does not exist, the investigator should use the grade or adjectives: Grade 1 (mild), Grade 2 (moderate), Grade 3 (severe), Grade 4 (life-threatening), or Grade 5 (fatal) to describe the maximum intensity of the adverse event. For purposes of consistency with the CTCAE, these intensity grades are defined in Table 7-1.

Grade	Adjective	Description
Grade 1	Mild	Sign or symptom is present, but it is easily tolerated, is not expected to have a clinically significant effect on the subject's overall health and well-being, does not interfere with the subject's usual function, and is not likely to require medical attention.
Grade 2	Moderate	Sign or symptom causes interference with usual activity or affect clinical status, and may require medical intervention.
Grade 3	Severe	Sign or symptom is incapacitating or significantly affects clinical status and likely requires medical intervention and/or close follow-up.
Grade 4	Life-threatening	Sign or symptom results in a potential threat to life.
Grade 5	Fatal	Sign or symptom results in death.

Table 7-1.Grading of Adverse Event Severity

The distinction between the seriousness and the severity of an adverse event should be noted. Severe is a measure of intensity; thus, a severe reaction is not necessarily a serious reaction. For example, a headache may be severe in intensity, but would not be classified as serious unless it met one of the criteria for serious events listed in Section 7.3.

7.3. Investigator Requirements and Instructions for Reporting Adverse Events and Serious Adverse Events to Gilead

Requirements for collection prior to study drug initiation:

After informed consent, but prior to initiation of study medication, the following types of events should be reported on the case report form (CRF/eCRF): all SAEs and adverse events related to protocol-mandated procedures.

Adverse Events

Following initiation of study medication until 30 days after last administration of study medication AEs, regardless of cause or relationship, must be reported to the CRF/eCRF database as instructed.

All AEs should be followed up until resolution or until the adverse event is stable, if possible. Gilead Sciences may request that certain AEs be followed beyond the protocol defined follow up period.

Serious Adverse Events

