8.6.2. Adverse Events

All adverse events will be listed. The focus of adverse event summarization will be on treatment emergent adverse events. A treatment-emergent adverse event is defined as an adverse event that onset in the period from the first dose of study treatment to 30 days after the permanent discontinuation of study treatment or that leads to permanent discontinuation of study treatment. Adverse events that occur before the first dose of study treatment or >30 days after the subject has been discontinued from study treatment will be included in data listings.

Adverse events will be classified using MedDRA (http://www.meddramsso.com) with descriptions by System Organ Class, High-Level Group Term, High Level Term, Preferred Term, and Lower-Level Term. The severity of adverse events will be graded by the investigator according to the CTCAE, Version 4.03 (http://evs.nci.nih.gov/ftp1/CTCAE/CTCAE_4.03_2010-06-14_QuickReference_5x7.pdf), whenever possible. If a CTCAE criterion does not exist for a specific type of adverse event, the grade corresponding to the appropriate adjective will be used by the investigator to describe the maximum intensity of the adverse event: Grade 1 (mild), Grade 2 (moderate), Grade 3 (severe), Grade 4 (life threatening), or Grade 5 (fatal). The relationship of the adverse event to the study treatment will be categorized as related or unrelated.

Treatment-emergent adverse events will be summarized. Summary tables will be presented to show the number of subjects reporting treatment-emergent adverse events by severity grade and corresponding percentages. A subject who reports multiple treatment-emergent adverse events within the same Preferred Term (or System Organ Class) is counted only once for that Preferred Term (or System Organ Class) using the worst severity grade. The summary will be presented in decreasing frequency of System Organ Class and Preferred Term of the 'Total' column. Within the same frequency, the AEs are ordered in the alphabetical order of System Organ Class and Preferred Term.

Separate listings and summaries will be prepared for the following types of treatment emergent adverse events:

- Study-drug-related adverse events
- Adverse events that are Grade \geq 3 in severity
- Adverse events leading to study treatment interruption and/or dose modification
- Adverse events leading to study treatment discontinuation
- Serious adverse events

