6.2.2. Analysis Methods for Secondary Efficacy Endpoints

Overall Remission (CR/CRi) rate, CR rate, PR rate, and Overall Response rate (CR, CRi, or PR) on or prior to other anticancer therapy and HSCT (if there is) at the end of induction will be summarized by dose level and overall. The number and percentage of subjects will be presented.

A by-subject listing of response assessment and EMD assessment will be provided by subject ID number (in ascending order) and visit (in chronological order).

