7.1.5. Treatment-Emergent Adverse Events

7.1.5.1. Definition of Treatment-Emergent Adverse Events

AEs which meet at least one of the following criteria are defined as Treatment-Emergent Adverse Events (TEAEs):

- Any AEs with onset dates on or after the start of study treatment and up to 30 days after the permanent discontinuation of the study treatment
- Any AEs leading to permanent discontinuation of study treatment

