7.2.1.1. Treatment-Emergent Laboratory Abnormalities

Treatment-emergent laboratory abnormalities are defined as values that increase at least 1 toxicity grade from baseline at any postbaseline time point, up to and including the date of last dose of study drug plus 30 days. If the relevant baseline laboratory value is missing, any abnormality of at least Grade 1 observed within the time frame specified above will be considered treatment emergent.

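### The safety tables run a fixed 30 days past the last dose with no cut at new anti-leukemia therapy or transplant, so events under a next regimen can enter the all-cause tables, although the SAP's response rates stop at that point.

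*Protocol*

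**What the plan says.** Every post-treatment safety window in the plan is a fixed 30 days.

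- Overall safety data (Protocol 8.6): everything from first dosing "up to 30 days after the date of last dose of study treatment will be summarized by dose level".
- TEAEs: Protocol 8.6.2 covers any "adverse event that onset in the period from the first dose of study treatment to 30 days after the permanent discontinuation of study treatment". SAP 7.1.5.1 likewise runs "up to 30 days after the permanent discontinuation of the study treatment". Both also admit any event that leads to permanent discontinuation.
- Laboratory abnormalities (SAP 7.2.1.1): any worsening by at least one grade "up to and including the date of last dose of study drug plus 30 days".
- Deaths (SAP 7.1.6.2): split at 30 days after the last dose.
- Collection (Protocol 7.3): "until 30 days after last administration of study medication AEs, regardless of cause or relationship, must be reported".

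None of these ends at the start of new anticancer therapy or HSCT. The response analysis does: SAP 6.2.2 reports the response rates "on or prior to other anticancer therapy and HSCT (if there is) at the end of induction".

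The plan foresees further therapy soon after study drug. The synopsis expects most transplant-eligible subjects who reach CR to go to HSCT or other curative therapy, and lists refractory disease and the start of new therapy among the events that end GS-9973. Protocol 6.7 places the end-of-treatment procedures before any new regimen. Protocol 6.7.2 then follows subjects for later treatment: "Information to be gathered includes ALL treatments, other malignancies, and survival".

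**The concern.** Salvage chemotherapy and transplant conditioning can themselves cause cytopenias, febrile neutropenia, infections and deaths. If either begins within 30 days of the last study dose, those events satisfy the TEAE definition and are reported by dose level under the study combination. How many there are would depend on how quickly subjects at each level move on, and not only on the dose. The SAP treats new therapy and HSCT as a boundary for efficacy but gives safety, the primary objective, no such boundary. Cohorts of 3 to 6 subjects leave little room to absorb even one such case.

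**Working it through.** **Figures in the plan.** The plan gives no figure for this effect. Its sample-size figures reproduce: 18/(1 − 0.10) = 20 enrolled. The 3+3 escalation probability, (1−p)³ + 3p(1−p)²(1−p)³, gives 0.906, 0.709, 0.494, 0.309, 0.172 and 0.082 at true DLT rates of 10% to 60%, matching Protocol Table 8-1 to two decimals. Neither changes under the fix, which concerns only a reporting window.

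**Which outputs are exposed.**

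| Output | Filter beyond timing | Exposed? |
|---|---|---|
| All TEAEs, Grade 3 or higher, TE SAEs, fatal TEAEs (SAP 7.1.6.1) | none by cause | yes |
| Deaths within 30 days (SAP 7.1.6.2) | none | yes |
| Related TEAEs by drug (SAP 7.1.3, 7.1.6.1) | investigator attribution; missing counts as related | partly protected |
| Laboratory grades (SAP 7.2.1, 7.2.1.1) | none by cause; worst of central and local grade used | only if sampled under the next regimen |
| DLTs (Protocol 3.3.1.1, 3.5) | study days 1 to 35; must be judged related | largely not |

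**Laboratory sampling.** Protocol 6.7 takes the end-of-treatment panel before a new regimen. Protocol 6.7.1 describes the 30-day follow-up as a contact and lists no laboratory tests, and Protocol Appendix 2 marks hematology and chemistry only through End of Treatment. SAP Appendix 1 also marks both at the 30-day follow-up. Laboratory exposure therefore comes mainly from unscheduled or local values, or from that sample in the SAP schedule.

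**Days under the next regimen.** Let g be the days free of new therapy after the last dose. The days of the window under the next regimen are 30 − g. The values of g are assumptions.

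- Stop at the end of Cycle 1: 7 + 28 = 35 days on treatment, and 35 + 30 = 65 counted days.
- Stop at the end of Cycle 2, with no break between cycles: 7 + 28 + 28 = 63, and 63 + 30 = 93 counted days.

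| g | 30 − g | share of 65 | share of 93 |
|---|---|---|---|
| 1 | 29 | 44.6% | 31.2% |
| 7 | 23 | 35.4% | 24.7% |
| 14 | 16 | 24.6% | 17.2% |

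Maintenance would lower these shares further. They are shares of calendar time and do not estimate bias in any table.

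**Effect of one subject.** If a subject's only qualifying event falls under the next regimen, removing it changes the incidence by 1/n: 33.3 points at n=3, 16.7 at n=6, 5.6 at n=18 and 5.0 at n=20.

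**Can a reader separate these events from the planned outputs?** Only in part. AEs and laboratory results are listed by subject in date order. However, SAP 7.4.2 does not class a medication begun after the last study dose as concomitant, so the next regimen is absent from that listing, and I find no SAP listing of subsequent anticancer therapy.

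**The case against.** Treatment-emergent is a label about timing and makes no causal claim. A fixed 30 days matches AE collection and does not discard delayed toxicity of the study drugs. SAP 7.1.3 asks for relatedness drug by drug, and SAP 7.1.6.1 tabulates related TEAEs, related Grade 3 or higher TEAEs and related SAEs, so an investigator can attribute an event elsewhere. The report is a descriptive, synoptic CSR of a Phase 1b whose expansion was cancelled. All of this stands. It limits the point to the all-cause tables and the death split, and it argues for adding a summary and not replacing one.

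Four stronger readings are tempting, and the documents do not support them.

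- That most subjects moved to another regimen within 30 days. A low response rate is stated. The number going on to further therapy, and its timing, are not. HSCT is anticipated only after CR, again without timing.
- That dose escalation or the MTD is contaminated. DLTs are confined to days 1 to 35 and need a judgment of relatedness. Protocol 8.1.2 names DLTs as the primary measure; only the synopsis adds other AEs and laboratory abnormalities.
- That laboratory abnormalities cannot be disentangled. They have no causality field, but they can be separated by date.
- That the plan as a whole cuts efficacy at new therapy. The cut is in SAP 6.2.2 only; Protocol 8.5.1 has none.

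It is also fair to object that SAP 6.2.2 does not mention a conditioning start date, so that date may not be recorded.

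**Conclusion.** The point holds in a limited form. Events under a next regimen begun within 30 days can enter the all-cause TEAE, Grade 3 or higher, serious, fatal and 30-day death tables, and nothing planned there separates them. The related-TEAE tables give partial protection, which is weaker where causality is left blank. The laboratory tables are exposed mainly through unscheduled or local values. The overall size is unknown because it depends on how many subjects start new therapy in the window and when. The day shares (about 25% to 45% if stopping after Cycle 1, 17% to 31% after Cycle 2) rest on the assumed gaps. The effect of one reclassified subject needs no such assumption and is large at 3 to 6 subjects per level. This is a worthwhile, inexpensive improvement and does not show that the planned 30-day tables are invalid.

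**What to change.** Keep the 30-day tables. In SAP 7.1.5.1 and 7.2.1.1, add a second window ending at the earlier of 30 days after the last dose and the day before the first new anticancer therapy or HSCT, using the conditioning start date if it is recorded. Repeat the overall TEAE, Grade 3 or higher, TE SAE, fatal TEAE and laboratory-grade tables on it. In SAP 7.1.6.2, split deaths within 30 days into before and after that date. Flag later events in the AE, SAE, death and laboratory listings. Reconcile the 30-day laboratory sample in SAP Appendix 1 with Protocol 6.7.1 and Appendix 2.

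The cost is a rerun of existing tables with dates that SAP 6.2.2 already requires; only a conditioning date might be new. SAP Section 1 allows a change made after finalization to be documented in the CSR. The downside is that delayed study-drug effects starting after new therapy appear only in the 30-day version, which is why both versions are kept.
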